2.4. Visit Windows

As subjects do not always adhere to the protocol visit schedule, the following rules are applied to assign actual visits to analysis visits. Listed below are the visit windows and the target days for each visit. The same definitions will apply to visits before or after the treatment end date using the Analysis Day as defined in Section 2.3 above. The time period description will be appended with '(On-Trt)' for post-baseline visits on or prior to the treatment end date. The time period description will be appended with '(Off-Trt)' for post-baseline visits after the treatment end date. If a subject has 2 or more actual visits in one visit window, the visit closest to the target day will be used as the protocol visit for that visit window. The other additional visit(s) will not be used in the summaries or analyses but they can be used for determination of clinically important endpoints. If 2 actual visits are equidistant from the target day within a visit window, the later visit will be used.

All assignments will be made in chronological order. Once a visit date is assigned to a visit window, it will no longer be used for a later time point except for the endpoint. Listed below (Table 1) are the visit windows and the target days for each visit defined in the protocol.

Table 1: Visit Windows for on and off-treatment Analysis

Scheduled Visit Number	Time period (label on output)	Time Interval (Day*)	Target Time Point (Day)
7	Baseline	-120 to 1	1
8	Week 2	2 to 22	15
9	Week 4	23 to 36	29
10	Week 6	37 to 50	43
11	Week 8	51 to 64	57
12	Week 10	65 to 81	71
13	Month 3	82 to 106	92
14	Month 4	107 to 134	120
15	Month 5	135 to 165	148
16	Month 6	166 to 211	183
17	Month 8	212 to 256	239
18	Month 9	257 to 288	274
19	Month 10	289 to 333	302
20	Month 12	334 to 410	365
21	Month 15	411 to 501	456
22	Month 18	502 to 592	547
23	Month 21	593 to 683	638
24	Month 24	684 to 774	729
25	Month 27	775 to 865	820
26	Month 30	866 to 956	911
27	Month 33	957 to 1047	1002
28	Month 36	1048 to 1138	1093
29	Month 39	1139 to 1229	1184
30	Month 42	1230 to 1320	1275
31	Month 45	1321 to 1411	1366
32	Month 48	1412 to 1502	1457
33	Month 51	1503 to 1593	1548
34	Month 54	1594 to 1684	1639
	Month >54	1685 to ∞	1685

* Relative to analysis reference start date if visit date is prior to or on the treatment end date. Relative to treatment end date if visit date is after treatment end date.

‘End point (On-Trt)’ is defined as the last available post-baseline result among the on-treatment visits. Unscheduled visit results are included in this definition and will be considered as the endpoint value if the unscheduled visit result is the last post-baseline result available among all on-treatment visits. ‘Baseline (Off-Trt)’ will be defined as the same as ‘End point (On-Trt)’. ‘End point (Off-Trt)’ is defined similarly to ‘End point (On-Trt)’ but based on off-treatment visits.

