## **9. STUDY EVALUATIONS**

### **9.1. Study Procedures**

#### **9.1.1. Overview**

The Time and Events Schedule summarizes the timing of efficacy, PK, biomarker, genomic, and safety measurements applicable to this study.

The Time and Events Schedule lists the month associated with each visit during the double-blind treatment phase. During this phase, subjects will visit the site at approximately every 2 weeks for the first 3 months (visit 2 weeks=2 weeks post-Day 1, visit Month 1=4 weeks post-Day 1, visit Month 1+2 weeks=6 weeks post-Day 1, Month 2=8 weeks post-Day 1, Month 2+2weeks=10

weeks post-Day 1, Month 3=13 weeks post-Day 1), monthly intervals from 3 months to 6 months (visit Month 4=17 weeks post-Day 1, Month 5=21 weeks post-Day 1, Month 6=26 weeks post-Day 1), with additional visits at Month 8, Month 9, Month 10, and Month 12 (Month 8=34 weeks post Dose-Day 1, Month 9=39 weeks post-Day 1, Month 10=43 weeks post-Day 1, Month 12=52 weeks post-Day 1), and then at 3-month (13-week) intervals through Month 54 (eg, visit Month 15=65 weeks post-Day 1, Month 54=234 weeks post-Day 1). A visit window of  $\pm 4$  calendar days will be allowed for visits at Months 1 and 2 of the double-blind treatment phase, while a visit window of  $\pm 12$  calendar days will be allowed for subsequent visits during this phase. All visits of the double-blind treatment phase are in principle single day visits, however, they may be performed over multiple days within the allowed visit window in the case of logistical issues or subject preference. The date of the visit should always be calculated from the baseline visit, not from the prior visit.

The time points for safety measures, PK measures, and biomarker measures may be changed by the sponsor (with or without affecting the overall frequency of these assessments) prior to and during the study based on newly obtained data (eg, IA results) to optimize evaluation of the safety, PK, and PK/PD profile of the study drug. These modifications may result in a change in the overall frequency of the safety measures or sample collections. The maximal total blood volume collected per subject will not be exceeded. In general, such modifications to the time points for key study parameters, where performed only to optimize evaluation of the actual safety, PK, or PK/PD profile of atabecestat will be documented in a note to file and included in the next following protocol amendment.

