5.2.2. Definition

The primary endpoint is the PACC change score.

The PACC change score at a time point is a composite of 4 standardized changes from baseline (two episodic memory tests, one timed executive function test, and a test of global cognition) at that time point as follows:

PACC change score = $Z1+Z2+Z3+Z4$, where

- $Z1 = (\text{change from baseline in FCSRT score} / \text{SD of the baseline FCSRT score})$, where the FCRST score is twice the number of correct free recalls in 3 trials plus the number of correct cued recalls in 3 trials from the Free and Cued Selective Reminding Test (FCSRT). See Section 5.4.1.1 for details of the FCSRT.
- $Z2 = (\text{change from baseline in WMS test score} / \text{SD of the baseline WMS test score})$, where the WMS test score is the total number of correct recalls after a 30-minute delay from the Wechsler Memory Scale (WMS) Logical Memory subtest (delayed paragraph recall). See Section 5.4.1.2 for details of the WMS Logical Memory subtest.
- $Z3 = (\text{change from baseline in DSS test score} / \text{SD of the baseline DSS test score})$, where the DSS test score is the number of correctly drawn symbols completed in 120 seconds from the Wechsler Adult Intelligence Scale (WAIS)-IV Coding subtest (also known as the Digit Symbol Substitution [DSS] test). See Section 5.4.1.3 for details of the WAIS-IV Coding subtest.
- $Z4 = (\text{change from baseline in MMSE total score} / \text{SD of the baseline MMSE total score})$, where the MMSE total score is the total number of correctly completed items on the Mini-Mental State Examination (MMSE). See Section 5.4.1.4 for details of the MMSE.

The PACC baseline score is the sum of the 4 components' standardized baseline value (baseline value / SD of baseline values). The PACC scores will be considered missing if more than 1 of its 4 components is imputed (see Section 5.1.2). Change from the off-treatment baseline (see Section 2.4) will be calculated. For off-treatment visits, however, the components will not be imputed. The PACC scores will be considered missing if any of the components is missing.

The scales contributing to the PACC all follow the same schedule: during screening, at the randomization visit, and every 6 months after randomization through Month 54 (or early termination).

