5.2.3. Analysis Methods

The primary analysis is based on the primary analysis set defined in Section 5.2.1 and uses an MMRM model. This relies on the Missing at Random (MAR) assumption: after accounting in the model for the effects of the covariates and for the available efficacy scores, the unobserved data have the same distribution as the observed data.

The PACC change score will be analyzed by an MMRM model based on observed data at on-treatment visits. The fixed terms for this model are treatment group, sex, country, APOE ε4 carrier status, education level, PACC baseline score, age at study entry, average hippocampal volume at baseline, time point (as a factor), and the interaction of treatment and time point. Subject is included as a random effect.

Comparisons between each atabecestat dose group and placebo will be performed at Months 6, 12, and 18 by using the appropriate contrasts based on this model. The Kenward-Roger approximation will be used to estimate the denominator degrees of freedom. Between-treatment differences in LS Means with the corresponding 95% confidence intervals (CIs) and p-values will be provided. If the unstructured covariance matrix results in a lack of convergence, starting values will be supplied using estimates from simpler structures. If this strategy does not result in

convergence then the following structures will be used in sequence: heterogeneous autoregressive of order 1 (ARH(1)), heterogeneous compound symmetry (CSH), and homogeneous compound symmetry (CS).

Plots of mean (\pm SE) PACC change score over time by treatment group will be provided for observed data and for estimates based on the MMRM.

For the off-treatment period, change of PACC and the components from off-treatment baseline will be summarized.

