5.4.1.8. Repeatable Battery for the Assessment of Neuropsychological Status (RBANS)

The RBANS is administered during screening prior to amyloid testing, 5 to 10 days before randomization, Month 3 after randomization, then every 6 months through Month 51 (or early termination, if the PACC components were administered at the subject's previous visit). The RBANS is a 20- to 25-minute battery developed for cognitive assessment, detection, and characterization of dementia in the elderly, as well as for neuropsychological screening for younger patients¹². Three versions of the RBANS will be administered in an alternating manner during the study. The RBANS includes 12 subtests that measure the following 5 indices:

Immediate Memory

The Immediate Memory index is composed of the List Learning and Story Memory subtests.

In the List Learning subtest, a list of 10 words is read and the subject is asked to immediately recall as many of the words as the subject can. Four trials of the same list of words are conducted. The List Learning total score is the sum of correctly recalled words over the 4 trials (range: 0 to 40).

In the Story Memory subtest, a short story is read and the subject is immediately asked to recall as much of the story as the subject can. Two trials of the same story are conducted. The Story Memory total score is the total number of items of information (out of 12) the subject correctly recalled over the 2 trials (range: 0-24).

Based on the List Learning and Story Memory total scores, an Immediate Memory Index Score is determined from a mapping table appropriate for the subject's age. For example, for a subject between 60-69 years with a List Learning total score of 30 and a Story Memory total score of 15, the Immediate Memory Index Score is 100. The Immediate Memory Index Score ranges from 40 to 152.

Visuospatial/Constructional

The Visuospatial/Constructional index is composed of the Figure Copy and Line Orientation subtests.

In the Figure Copy subtest, subjects are shown a figure composed of 10 items and are asked to immediately copy the figure from memory. For each figure item, it is determined whether the item was correctly drawn and correctly placed. The Figure Copy total score is the sum of the number of correctly drawn and number of correctly placed items (range: 0-20).

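### SAP Table 1 uses one set of visit windows for all data, so some Month 3 and Month 9 RBANS scores lose their time point; PACC is affected only well outside the protocol visit tolerance

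*SAP*

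**What the plan says.** SAP 2.4 says that "the following rules are applied to assign actual visits to analysis visits", and introduces its only window table with "Listed below (Table 1) are the visit windows and the target days for each visit defined in the protocol". No scale has windows of its own. Where two or more visits fall in one window, the visit closest to the target day is kept and the others are left out of summaries and analyses.

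The two cognitive batteries alternate. SAP 5.4.1.8 schedules RBANS at "Month 3 after randomization, then every 6 months through Month 51". SAP 5.2.2 schedules the PACC components "every 6 months after randomization through Month 54 (or early termination".

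The PACC model in SAP 5.2.3 has "time point (as a factor), and the interaction of treatment and time point", and "Comparisons between each atabecestat dose group and placebo will be performed at Months 6, 12, and 18". SAP 5.4.2 applies a similar model to RBANS, with time continuous for endpoints measured at unequally spaced time points.

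In protocol 9.1.1, visits after Month 2 have a tolerance of 12 days either way ("calendar days will be allowed for subsequent visits during this phase"), and nominal timing runs in weeks from Day 1 ("Month 3=13 weeks post-Day 1").

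**The concern.** The table is dense in the first year because safety visits are dense then, with visits at Months 4, 5, 8 and 10 and two-weekly visits before Month 3. Each of these takes part of the calendar away from the neighbouring cognitive visit. A score falling outside the narrow window of its own visit takes the label of a visit at which that scale is not scheduled, and the SAP has no rule for returning it.

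Such a score would not count at its time point. In addition, the closest-visit rule does not ask whether the closest visit has a result for the scale, so read literally a nearer visit without the scale displaces the visit that has the score. SAP 5.1.1 reports that 80% of randomized subjects had no more than 12 months of treatment, so most of the data lie where the windows are narrowest.

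**Working it through.** **1. Reproduce Table 1.** Target day = 7 × nominal weeks + 1. Month 3: 7 × 13 + 1 = 92. Month 6: 7 × 26 + 1 = 183. Month 9: 7 × 39 + 1 = 274. Month 12: 7 × 52 + 1 = 365. Each upper limit is the midpoint, rounded down, between adjacent targets over all clinic visits. Month 3 to Month 4: (92 + 120)/2 = 106. Month 9 to Month 10: (274 + 302)/2 = 288. Month 6 to Month 8: (183 + 239)/2 = 211. All of these match the table, so the limits are set by the neighbouring clinic visit, whatever is assessed there.

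**2. Room on each side of the target, against the protocol's ±12 days.**

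| Scale and visit | Window | Target | Days early allowed | Days late allowed | Label one day later |
|---|---|---|---|---|---|
| RBANS Month 3 | 82–106 | 92 | 10 | 14 | Month 4 |
| RBANS Month 9 | 257–288 | 274 | 17 | 14 | Month 10 |
| RBANS Month 15 | 411–501 | 456 | 45 | 45 | Month 18 |
| PACC Month 6 | 166–211 | 183 | 17 | 28 | Month 8 |
| PACC Month 12 | 334–410 | 365 | 31 | 45 | Month 15 |
| PACC Month 18 | 502–592 | 547 | 45 | 45 | Month 21 |

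None of the labels in the last column is a scheduled visit for that scale.

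**3. Inside tolerance.** The only conflict is RBANS at Month 3. The earliest compliant day is 92 − 12 = 80, but the window opens on Day 82. Days 80 and 81 belong to Week 10 (Days 65–81, target 71). If the subject also attended on Day 71, that visit is 0 days from target and the Day 80 visit is 9 days away, so the closest-visit rule drops the visit with the RBANS.

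**4. Outside tolerance.** RBANS at Months 3 and 9 is relabelled from 15 days late, only 3 days past the tolerance. PACC at Month 6 is relabelled from 29 days late or 18 days early; at Month 12 from 46 late or 32 early; at Month 18 from 46 either way.

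**5. How often.** The documents give no distribution of visit timing. As an illustration only, assume normal timing error centred on target. The chance of exceeding k days on one side is 1 − Φ((k + 0.5)/SD).

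| Assumed SD (days) | Outside ±12 | RBANS Month 3 or 9, 15+ late | RBANS Month 3, 11+ early | PACC Month 6, 29+ late | PACC Month 6, 18+ early |
|---|---|---|---|---|---|
| 7 | 7.4% | 1.9% | 6.7% | under 0.01% | 0.6% |
| 10 | 21.1% | 7.4% | 14.7% | 0.2% | 4.0% |
| 14 | 37.2% | 15.0% | 22.7% | 2.1% | 10.6% |

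PACC at Month 12, 46 or more days late, stays below 0.1% throughout. The SD of 14 would mean that more than a third of visits miss the tolerance, so it is a pessimistic case.

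**6. What happens to a relabelled score.** Protocol 11.3.1 limits the visit factor to visits scheduled for the measure, which would leave the record out. SAP 5.2.3 does not repeat that limit; read alone, it would add a level. Carry-forward (SAP 5.1.2) does not rescue a PACC whose components were all taken at the late visit, because SAP 5.2.2 sets the composite to missing when more than one component is imputed.

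**The case against.** The strongest reply is that the windows do their job: every late assessment within tolerance keeps its label, PACC has generous room, and narrow windows keep scores near their nominal time. The last on-treatment result also survives as the on-treatment end point, whatever its label. All of this stands, and it limits the point to RBANS at Months 3 and 9. It does not answer the compliant Day 80 or 81 RBANS or the visit-level selection rule.

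Four stronger readings are tempting and are not supported.

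- **Any late RBANS or PACC is mislabelled.** Step 2 shows that this is not so.
- **Near-empty levels will break the unstructured model.** An extra level arises only if unscheduled labels are kept as factor levels, which protocol 11.3.1 does not do. For RBANS it also depends on whether the continuous-time rule in SAP 5.4.2 applies. That is arguable, since post-baseline spacing is equal but the first interval is shorter. If convergence did fail, SAP 5.2.3 first tries starting values from simpler structures.
- **The long runs of days with no RBANS or PACC label measure the loss.** They mostly count days on which no test is due. A count of lost scores out of the 557 randomized would need a lateness rate that the documents do not give, and recently randomized subjects may not have reached Month 3 on treatment.
- **Extra liver blood draws displace cognitive visits more often on active drug.** Protocol Attachment 3 does require frequent rechecks, but SAP 2.4 does not say whether such draws count as visits for an efficacy scale.

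**Conclusion.** The point holds as a limited defect in a stated rule. One table built for safety visits is applied to scales given every six months. It misplaces an RBANS 15 or more days late at Months 3 and 9 and two protocol-compliant early days at Month 3, and it lets a visit without the scale displace one with it. For PACC, only visits far outside tolerance are affected, so the effect on the primary endpoint is probably small. The number of scores involved cannot be stated from the documents; the rates in step 5 rest on assumed timing errors. SAP 1.3 and 5.1.1 make all comparisons exploratory, without formal hypothesis testing, so no confirmatory conclusion depends on this. It is a worthwhile tidy-up of low severity.

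**What to change.** Keep Table 1 for safety data. For efficacy scales, add windows built from each scale's own schedule and capped at the 45 days either side that Table 1 already uses for its 3-monthly visits (target − 45 to target + 45):

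- PACC: Month 6 = Days 138–228, Month 12 = 320–410, Month 18 = 502–592.
- RBANS: Month 3 = Days 47–137, Month 9 = 229–319, Month 15 = 411–501.

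Apply the same construction to later visits and to the other efficacy scales. Add two sentences: the closest-visit rule is applied among visits with a non-missing result for that scale; and, as in protocol 11.3.1, only visits scheduled for the measure are MMRM levels.

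The cap is deliberate. Splitting at midpoints without it would make PACC Month 6 run from Day 2 to Day 274, which is too wide. Its consequence is that a score between windows (for PACC, Days 229–319 or 411–501) still has no time point and is used only for the on-treatment end point; the SAP should say so.

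The cost is one extra SAP table, and a few scores assigned further from target than now: up to 45 days late instead of 14 for RBANS at Months 3 and 9, and 45 instead of 28 for PACC at Month 6. These can be flagged.

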- j Serves as baseline assessment and will be performed between Day -10 and Day -5 and at least 2 days after the amyloid disclosure visit.
- k At selected centers only.
- l Amyloid PET imaging or lumbar puncture to collect a CSF sample for determination of A $\beta$ 1-42 levels, or both, will be performed to assess elevated amyloid accumulation at study entry and to determine eligibility. Elevated amyloid accumulation can be determined by results for either of these biomarker evaluations, but the decision on which tests are going to be done must be made before either result is available. The amyloid disclosure visit will be performed when both results, if applicable, are available.
- m Only at sites capable of processing PBMC samples.
- n MRI and PET collection can be performed at the same visit based on-site preference, and results must be available during screening phase to confirm subject eligibility.
- o For safety; both volumetric and task-free functional MRI.
- p No subjects will receive more than 3 amyloid PET scans during the study.

Phase	Double-blind Treatment Phase																												Early Termination	Follow up Visit c	
	Month (M) a	M0 (D1)	W2*	M 1	M1 +2W	M 2	M2 +2W	M 3	M 4	M 5	M 6	M 8	M 9	M 10	M 12	M 15	M 18	M 21	M 24	M 27	M 30	M 33	M 36	M 39	M 42	M 45	M 48	M 51			M 54
Visit Window (± days)	0	± 2	± 4	± 2	± 4	± 2	± 12	± 12	± 12	± 12	± 12	± 12	± 12	± 12	± 12	± 12	± 12	± 12	± 12	± 12	± 12	± 12	± 12	± 12	± 12	± 12	± 12	± 12	± 12		
Visit Number	7	8	9	10	11	12	13	14	15	16	17	18	19	20	21	22	23	24	25	26	27	28	29	30	31	32	33	34		35	
Study Procedures																															
Vital signs (supine and standing blood pressure, pulse)	X d						X			X		X		X		X		X		X		X		X		X		X	X	X	
Triplicate 12-lead ECG i	X d		X				X			X				X		X		X		X		X		X		X		X	X	X f	
Height																												X	X		
Weight	X d									X				X		X		X		X		X		X		X		X	X	X	
Temperature	X d						X			X		X		X		X		X		X		X		X		X		X	X	X f	
Assessment of Psychological Well Being	X						X					X			X		X		X		X		X		X		X	X	X	X	
C-SSRS (since last visit)	X d	X	X	X	X	X	X	X	X	X	X	X	X	X	X	X	X	X	X	X	X	X	X	X	X	X	X	X	X	X	X
Clinical Laboratory Assessments																															
Hematology and chemistry	X	X	X	X	X	X	X	X	X	X	X	X	X	X	X	X	X	X	X	X	X	X	X	X	X	X	X	X	X	X	X f

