**Footnotes:**

\* Note this visit is to occur approximately 2 weeks after randomization.

a Timing of all study visits postbaseline should be calculated based on the difference in time from the baseline visit, not from the prior study visit. During this phase, subjects will visit the site approximately every 2 weeks for the first 3 months (visit 2W=2 weeks post-D1, visit M1=4 weeks post-D1, visit M1+2 weeks=6 weeks post-D1, M2=8 weeks post-D1, M2+2weeks=10 weeks post D1, M3=13 weeks post-D1), at monthly intervals from 3 months to 6 months (M4=17 weeks post-D1, M5=21 weeks post-D1, M6=26 weeks post-D1), additional visits at Month 8, Month 9, Month 10, and Month 12 (M8=34 weeks pose dose-D1, M9=39 weeks post-D1, M10=43 weeks post-D1, M12=52 weeks post-D1, and then at 3-month (13-week) intervals through Month 54 (eg, visit M15=65 weeks post-D1, M54=234 weeks post-D1).

b If a subject is withdrawn from the study, he/she will be asked to have the Early Termination Visit assessments performed. The subject will complete the posttreatment phase (follow-up visit) within 7 to 28 days following the last dose of study drug or the Early Termination Visit assessments (if performed), whichever comes last. Subjects who discontinue study treatment but elect to remain in the study will continue to have study assessments performed through Month 54; the focus will be on collecting primary and secondary clinical outcome measures and reducing other assessments. In both cases (withdrawal from the study or discontinuation of study treatment but remaining in the study), the disposition status should be completed for the subject.

c Follow-up Visit assessments to be performed 7 to 28 days after last dose of study drug.

d Predose.

e Between 7:00 and 11:00 AM daily, subjects should self-administer study drug (atabecestat/placebo) with a glass (200 mL) of noncarbonated water. On Day 1, the first dose of study drug can take place at any time during the day provided all predose assessments have been performed. At visits specified in the table, , subjects should self-administer the study drug on-site (at the study center/clinic).

f Only if any clinically significant abnormalities observed on previous occasion.

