## 2. Follow-up Blood Sampling and Ongoing Contact with Medical Monitor

After the initial investigation, regardless of results, serum chemistry is to be performed (using the central lab retest kit) per the schedule below (Table 3) and close contact with the medical monitor with a minimal contact frequency (as outlined in the table) is also expected.

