2.3. Reference Start Date and Analysis Phases

The analysis reference start date (Study Day 1) is defined as the date of the first dose of study medication. The Study Day of an event start or stop date is defined relative to the analysis reference start date as:

- Event date – analysis reference start date + 1, if the visit/event date is on or after the analysis reference start date, or

- Event date – analysis reference start date -1, if the visit/event date is before the analysis reference start date

Study Days <1 will be considered in the Screening analysis phase; Study Days \geq 1 (there is no Study Day 0) will be considered in the Double-blind analysis phase.

For visit dates prior to, or on, the date of the last dose of study medication, an Analysis Day will be defined as above relative to the analysis reference start date. For visit dates after the treatment end date, an Analysis Day is defined relative to the treatment end date as: Visit date – treatment end date + 1.

- Analysis reference start date (date of first dose as above) for all timepoints after first dose (whether before or after last dose)
- For assessments after last dose, use last observation before last dose as the reference time point.

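### SAP Table 1 opens the Month 3 window two days later than the protocol allows, and the closest-visit rule is worded per visit date, not per assessment

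*SAP*

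**What the plan says.** **Protocol timing.** Footnote a of the double-blind Time and Events Schedule gives "M2+2weeks=10 weeks post D1" and "M3=13 weeks post-D1". The schedule's window row allows ±2 days for the visit two weeks after Month 2 (the SAP's Week 10) and ±12 days from Month 3 onward. Section 9.1.1 gives ±4 days for Months 1 and 2, and says that ±12 "calendar days will be allowed for subsequent visits during this phase". The same section says of visits that "they may be performed over multiple days within the allowed visit window in the case of logistical issues or subject preference".

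**SAP windows.** Section 2.3 sets the day count: "The analysis reference start date (Study Day 1) is defined as the date of the first dose of study medication". Table 1 in section 2.4 gives Week 10 as Days 65 to 81 (target 71) and Month 3 as Days 82 to 106 (target 92). On multiple visits the rule is: "If a subject has 2 or more actual visits in one visit window, the visit closest to the target day will be used". Ties go to the later visit. The remaining visits are left out of summaries and analyses but may still inform clinically important endpoints. Visits are assigned in chronological order, and an assigned date cannot serve a later time point except the endpoint.

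**Extra laboratory dates.** Attachment 3 of the protocol adds retests after a liver enzyme elevation: "After the initial investigation, regardless of results, serum chemistry is to be performed". The frequency runs from twice weekly down to monthly.

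**The concern.** Two separate weaknesses sit in the same section of the SAP.

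First, a site can follow the protocol exactly and still have its Month 3 visit classed as Week 10. Month 3 is the first post-baseline RBANS. RBANS index and total scores and the ADCS-ADL-PI totals go into between-group mixed models (SAP 5.4.2), and none of these is scheduled at Week 10. By-visit summaries of CFI-a, ECG and vital signs at Month 3 are exposed in the same way.

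Second, the rule speaks of visits and visit dates. It does not say whether a visit spread over several days is one visit or several, whether an unscheduled laboratory draw is a visit, or whether selection is made for each assessment. Under a literal reading, a laboratory-only date nearer the target displaces the date on which PACC or RBANS was done. This can happen at any window, including Months 6, 12 and 18, where PACC is compared between groups. SAP 5.1.2 would then treat all four PACC components as missing and carry earlier values forward. Since more than one component would be imputed, SAP 5.2.2 sets the PACC to missing although it was observed. Two programmers could build different datasets from the same text.

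**Working it through.** **Inputs.** Visit weeks and tolerances: protocol Time and Events Schedule (window row and footnote a) and section 9.1.1. Day count: SAP 2.3, first dose = Day 1. Windows and targets: SAP Table 1.

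**Step 1: reproduce Table 1.** Target day = 7 × weeks + 1.
- Week 10: 7 × 10 + 1 = 71
- Month 3: 7 × 13 + 1 = 92
- Month 4: 7 × 17 + 1 = 120

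All 27 post-baseline targets, Week 2 to Month 54, reproduce exactly. The boundaries are midpoints of adjacent targets: (71 + 92)/2 = 81.5, which gives 81|82, and (92 + 120)/2 = 106. So 82 to 106 is what the SAP's own method yields.

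**Step 2: compare protocol and SAP windows.**

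| Visit | Target ± tolerance | Protocol days | SAP days | Contained? |
|---|---|---|---|---|
| Week 8 | 57 ± 4 | 53–61 | 51–64 | yes |
| Week 10 | 71 ± 2 | 69–73 | 65–81 | yes |
| Month 3 | 92 ± 12 | 80–104 | 82–106 | **no: Days 80, 81** |
| Month 4 | 120 ± 12 | 108–132 | 107–134 | yes |
| Month 5 | 148 ± 12 | 136–160 | 135–165 | yes |
| Month 6 | 183 ± 12 | 171–195 | 166–211 | yes |

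The other 21 visits are also contained. Month 3 alone fails, because the Week 10 to Month 3 gap is only 21 days and its midpoint lies 10.5 days before the Month 3 target, less than the 12 days allowed.

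**Step 3: what happens on Days 80 and 81.** Such a visit lies 80 − 71 = 9 or 81 − 71 = 10 days from the Week 10 target. An on-schedule Week 10 visit (Days 69 to 73) is at most 2 days away and always wins. The Month 3 visit is then excluded from by-visit analyses. With no competing visit it is kept, but labelled Week 10.

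**Step 4: size of the gap.** 2 of 25 permitted days = 8%. The documents give no distribution of visit dates, so any count is an assumption:

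| Assumed visit dates within Days 80–104 | Share on Days 80–81 | × 557 randomized |
|---|---|---|
| Centred on Day 92, SD 5 | 1.2% | about 7 |
| Centred on Day 92, SD 6 | 2.2% | about 12 |
| Centred on Day 92, SD 8 | 4.0% | about 22 |
| Uniform | 8% | about 45 |

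These are ceilings under each assumption, because they suppose that all 557 attended Month 3 on treatment.

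**Step 5: the per-visit wording.** Illustration at Month 6 (target 183): PACC on Day 177 and bloods on Day 182, both within Days 171 to 195. The distances are 183 − 177 = 6 and 183 − 182 = 1. If each date is a visit, Day 182 is selected and the PACC date is excluded. With bloods on Day 184 and PACC on Day 190 the distances are 1 and 7, with the same result. What goes is the date farther from target, whichever came first. For two consecutive days at Month 3 starting on Days 82 to 103, the first day is dropped for starts on 82 to 91 (10 of 22) and the second for starts on 92 to 103 (12 of 22).

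**The case against.** The strongest reply is that the boundary follows a consistent midpoint method, that Day 80 really is nearer to Week 10 (9 days) than to Month 3 (12 days), and that little depends on it. Most of the second part stands. Excluded visits still count for clinically important endpoints, and the on-treatment endpoint takes the last available result (SAP 2.4). Maximum QTc categories (SAP 6.3) and liver enzyme criteria (SAP 6.1.1) are not taken from the visit selected for a window. PACC is not scheduled at Month 3, so the boundary cannot affect it. PK samples are taken at Month 3, but SAP 7.1 plans no analysis of PK parameters. The midpoint argument explains the cut-off but does not reconcile it with a tolerance that the protocol grants.

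On the selection rule, protocol 9.1.1 treats a visit spread over several days as still one visit, and SAP 2.4 names unscheduled results explicitly only for the endpoint. A sensible programmer might therefore never drop a PACC. That is fair: this is an ambiguity that permits loss, not a demonstrated loss.

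A reader might infer that the loss falls more on the active arms, because retests follow ALT or AST elevation, an identified adverse drug reaction. Section 1.4 of the protocol reports 11 subjects above 3×ULN in studies longer than one month: 9 on active drug, 1 on placebo and 1 blinded. The documents do not carry the inference that far. It requires laboratory-only dates to count as visits, and no frequency of such dates near a cognitive visit is given. Subjects discontinued under the liver rules move to off-treatment windows counted from the treatment end date, where efficacy is only summarised descriptively (SAP section 5). Lower-grade retests in subjects who stay on treatment could compete, but neither size nor direction can be established.

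**Conclusion.** The mismatch is exact: SAP Table 1 excludes two protocol-compliant days from Month 3, and no other post-baseline visit has this problem. The result is exclusion from by-visit analyses when an on-schedule Week 10 visit exists, and a Week 10 label otherwise. The calculation takes the ±2 day Week 10 tolerance from the schedule's window row; section 9.1.1 does not list that visit separately. The consequence is limited mainly to Month 3 RBANS and ADCS-ADL-PI, plus by-visit CFI-a, ECG and vital sign summaries.

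The selection rule is a separate weakness. It could reach PACC, but only if split-visit days or unscheduled laboratory draws are treated as visits. Its frequency and any imbalance between arms cannot be determined from the documents.

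SAP 5.1.1 makes all comparisons exploratory, and section 1.3 plans no formal hypothesis testing. The impact is minor, but the correction is worth making because it keeps observed, compliant data at almost no cost.

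**What to change.** 1. In SAP Table 1, for on-treatment windows only, set Week 10 to Days 65–79 and Month 3 to Days 80–106. Both protocol windows (69–73 and 80–104) are then contained. Off-treatment windows can stay as they are, since they count from the treatment end date and the protocol's Month 3 tolerance does not apply to them.
2. In SAP 2.4, state that the closest-to-target rule is applied separately for each assessment or parameter, among dates in the window with a non-missing result for it. This settles split visits and laboratory-only dates together.

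**Cost.** Two boundary values and one sentence, with no new data. The drawback is that a Week 10 visit made on Day 80 or 81 would be labelled Month 3. Such a visit is at least 80 − 73 = 7 days beyond its own tolerance, so this should be rare. The 79|80 cut also departs from the midpoint method at one boundary, which a footnote to Table 1 can explain.
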